8.8.3 Clinical Laboratory Evaluations

Absolute and change from baseline values of laboratory parameters(viz. Total bilirubin, Hemoglobin, Alkaline phosphatase, Platelet count, ALT, Total WBC, AST, Absolute neutrophil count, GGT, creatinine) will be presented using descriptive statistics (n, mean, median, standard deviation, minimum and maximum values) for each cycle for each treatment group and overall.

The laboratory data will also be listed.

A separate listing of patients with abnormal laboratory test values will also be presented. Based on the available data which is captured in the database, the laboratory data will be listed for the following clinical laboratory parameters:

Hematology	Chemistry Panel I	Chemistry Panel II	Urinalysis	Other
Hematocrit	Total bilirubin	Total Cholesterol	Blood	Serum β-hCG
Hemoglobin	Alkaline phosphatase	Triglyceride (TG)	Glucose	Urine pregnancy test
Platelet count	ALT	LDL	Protein	PT and INR
WBC (Total and differentials)	AST	HDL	Specific gravity	Serology (Hepatitis B, Hepatitis C, HIV)- Historical data is acceptable.
Absolute neutrophil count	LDH	T3,T4,TSH	Microscopic exam ^b	
	GGT			
	Blood glucose			
	Albumin			
	Total protein			
	Urea or BUN ^a			
	Creatinine			
	Sodium			

CONFIDENTIAL

Potassium			
Calcium			
Phosphorous			
Chloride			

^a Blood Urea Nitrogen is preferred, if not available Urea may be tested.

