1.4 Clinical Experience

As of 20th April 2021, a total of 169 patients with relapsed/refractory hematological malignancies (viz. CLL, PTCL, CTCL and iNHL) have been exposed to tenalisib in either single agent or combination studies; 35 patients in RP6530-1301 study, 58 patients in RP6530-1401 study, 2 patients in RP6530+Pembrolizumab-1701 study, and 33 patients RP6530+Romidepsin-1805 study, 20 patients in RP6530-1802 study, 21 patients in RP6530-1901 study. A total of 16 patients have been rolled over to compassionate study (RP6530-1803); 4 from RP6530-1401 study, 5 from RP6530+Romidepsin-1805 study and 7 from RP6530-1901 study. In addition, 18 healthy volunteers were exposed to tenalisib in food effect study (RP6530-1501).

• Safety:

169 patients have received tenalisib at doses ranging from 25-1200 mg BID. Tenalisib is generally well tolerated in patients with hematological malignancies (at doses ranging from 25 mg BID to 1200 mg BID) and aggressive lymphomas such as TCL (at doses ranging from 200 mg BID to 800 mg BID). The most frequently reported related AEs (all grades) that occurred in more than 10% of patients included alanine aminotransferase (ALT) increased, aspartate aminotransferase (AST) increased (15.6% each) and diarrhea (11.9%). The most frequently reported related Grade ≥3 AEs were ALT increased, AST increased (7.4% each) and neutropenia (4.4%). Other Grade ≥3 laboratory abnormalities included gamma-glutamyl transferase (GGT) increased, International normalized ratio (INR)

CONFIDENTIAL Page 19 of 66

increased, hyperglycemia and hypertriglyceridemia reported in one patient each. Hypophosphatemia and thrombocytopenia were reported in two patients.

Pharmacokinetics:

In RP6530-1301 study, pharmacokinetics (PK) was evaluated in patients with hematological malignancies at doses ranging from 25-1200 mg BID and in TCL at doses ranging from 200 to 800 mg BID. Maximum systemic exposures assessed by AUC_{0-t} as determined on Cycle 1 Day 1 (C1D1) were found at these doses. Tenalisib showed rapid absorption (between 0.5 and 2 h), with C_{max} and AUC_{0-t} increasing proportionately with dose on C1D1. There was no significant accumulation between C1D1 and C2D1. Trough concentrations did not show any specific trends from one day to the other even though concentrations increased generally with doses. $T_{1/2}$ were similar for all dose levels.

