3.4.5 Precautions and Risks Associated with Investigational Product

- Monitoring of liver enzymes and levels of TSH, T3, and T4 in patients receiving tenalisib is recommended based on target organ toxicity. Patients will be monitored for increased ALT/AST, skin rash, neutropenia as these are reported with tenalisib. In addition, events like enteritis (colitis), pneumonia/pneumonitis would also be looked for as they have been reported with other PI3K inhibitors. Tenalisib elicits no photo instability upon exposure to ultraviolet (UV) radiations. However, in absence of in-vitro data, possibility of photo-toxicity with tenalisib cannot be ruled out.
- Tenalisib shows inhibition of CYP3A4 enzyme. Therefore, concomitant administration of tenalisib with predominant CYP3A4 substrates (e.g., calcium channel blockers,

CONFIDENTIAL Page 26 of 66

warfarin, carbamazepine, macrolide antibiotics, lovastatin, simvastatin, terfenadine) may reduce clearance of these drugs increasing the risk of adverse events.

- Similarly, as tenalisib is inhibited by CYP3A4/5 and CYP2C9, there is possibility of drug interaction with inhibitors or inducers of CYP3A4 and CYP2C9. If concomitant treatment with these drugs is clinically warranted, careful observation of the patient is advised. Strong inhibitor or inducers should be avoided as directed in *Section 5.3* on prohibited medication. Please refer to the recent Investigator Brochure for additional safety information. [14]

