| SAE evaluation | X | X | X | X | X | X | X | - | X | X |
| Concomitant medication | X | X | X | X | X | X | X | - | X | X |

Foot notes:

- 1. Patient should be re-consented, if informed consent is obtained > 30 days prior to the initiation of trial treatment. The first day of tenalisib administration will be considered as C1D1.
- 2. Demographic profile will include age, sex and race.
- 3. Detailed history will be taken at screening that includes history of cancer, past history, no of prior therapies and prior medication (in last 4weeks); and other medical history. Patient's medical record must include prior treatments received, dates of administration, response to prior therapies and date of progression.
- 4. Vitals will include pulse (sitting/supine); blood pressure (sitting/supine); respiratory rate and oral temperature. Vitals will be done at pre-dose at all visits.
- 5. Weight will be measured at all visits. Height to be measured at screening only.
- 6. Physical examination will include systemic examination (General Appearance, HEENT, neck, cardiovascular, lungs, abdomen, extremities, neurological, skin, and musculoskeletal). Complete physical examination will be done at screening visit. At subsequent visits, abbreviated examination will be done depending on the assessment of tumour.
- 7. This will include Hb, complete blood count, total leucocyte and differential count and platelet count. Additional investigations will be performed if clinically indicated. Hematology must be done ≤ 7 days prior to initiation of treatment. However, if these initial examinations are obtained within 72 hours of C1D1; they do not have to be repeated.
- 8. Chemistry Panel I include blood glucose, albumin, total protein, total bilirubin, ALP, AST, ALT, GGT, LDH, urea or blood urea nitrogen, creatinine, sodium, potassium, chloride, calcium, phosphorus. These tests must be done ≤ 7 days prior to initiation of treatment. However, if these initial examinations are obtained within 72 hours of C1D1; they do not have to be repeated. These tests will be performed at supplementary visits if clinically indicated.
- 9. Chemistry Panel II includes total cholesterol, TG, LDL, HDL, T3, T4 and TSH. These tests must be done ≤ 7 days prior to initiation of treatment. However, if these initial examinations are obtained within 72 hours of C1D1; they do not have to be repeated. These tests will be performed at supplementary visits if clinically indicated.

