- 19. All visits will be done monthly from Cycle 3 onwards for 24 months (e.g. C4, C5, C6.... C26).
- 20. All visits for efficacy assessments will be done at 8-weekly intervals (± 7 days) for 24 months (e.g.C5, C7.... C26).
- 21. All patients will undergo the end-of-treatment (EOT) assessments within 7 days after last dose of study drug or discontinuation.
- 22. Patients must be followed telephonically for adverse events for 30 calendar days after the last dose of study drug.

CONFIDENTIAL Page 40 of 66

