7.4.3 Abnormal Laboratory Values

Any grade 3 or 4 laboratory abnormalities and clinically significant grade 1 or 2 laboratory value(s) should be recorded as an AE. Isolated laboratory abnormality without clinical significance should not be captured as AE if confirmed by the investigator. If an abnormal laboratory value or vital sign is associated with clinical signs and/or symptoms, the sign or symptom should be reported as an AE, and the associated laboratory value or vital sign should be considered additional information that must be collected on the relevant eCRF. If the laboratory abnormality is a sign of a disease or syndrome, only the diagnosis needs to be recorded on the SAE Report Form or AE eCRF.

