Visit/	Actual values	Change from baseling	ne Actual values	Change from baseline	Actual values	Change from baseline
Statistics		values		values		values
Baseline						
N	XX		XX		XX	
Mean	x.xxx		X.XXX		X.XXX	
SD	x.xxxx		X.XXXX		X.XXXX	
Median	x.xxx		X.XXX		X.XXX	
Min, Max	X.XX, X.XX		x.xx, x.xx		x.xx, x.xx	
Cycle 1 Day 1						
N	XX	XX	XX	XX	XX	XX
Mean	x.xxx	X.XXX	X.XXX	X.XXX	X.XXX	X.XXX
SD	x.xxxx	X.XXXX	X.XXXX	X.XXXX	X.XXXX	X.XXXX
Median	x.xxx	X.XXX	X.XXX	X.XXX	X.XXX	X.XXX
Min, Max	x.xx, x.xx	X.XX, X.XX	x.xx, x.xx	x.xx, x.xx	x.xx, x.xx	x.xx, x.xx

Continue for all visits and parameters

The baseline measurement is the last pre-treatment measurement taken on or before Cycle 1 Day 1

Only scheduled visits are included in the table.

EOT: End of Treatment; NE: Non-Estimable.

Reference Listing 16.2.x.x

Program: xx.sas Table Generation: ddmmmyyyy hh:mm:ss

Use same format for

Table 14.3.2.2 Descriptive Summary of Biochemistry parameters - Safety Analysis Set

CONFIDENTIAL Page 55 of 106 Document Date: 12MAY2023. ST-AD-032 version 01

Page xx of yy

Table 14.3.3.1 Descriptive Summary of Vital Signs - Safety Analysis Set

Note - Please remove the column for change from baseline.

Add footnote-"Vitals is collected at Pre-dose during treatment visits"

Table 14.3.4.1 Descriptive Summary of ECG - Safety Analysis Set

Document Date: 12MAY2023.

Note - Please remove the column for change from baseline.

Add footnote-"ECG is collected at Pre-dose during treatment visits"

Protocol RP6530-2101 Table 14.3.4.2 Summary of Abnormal ECG results Safety Analysis Set Page xx of yy

		Tenalisib 800 mg BID	Tenalisib 1200 mg BID	Overall
Visit	Criteria	(N=xx)	(N=xx)	(N=xx)
		n (%)	n (%)	n (%)
Baseline	Clinically significant	xx (xx.x)	xx (xx.x)	xx (xx.x)
	Not clinically significant	xx (xx.x)	xx (xx.x)	xx (xx.x)
Cycle 1 Day 15	Clinically significant	xx (xx.x)	xx (xx.x)	xx (xx.x)
	Not clinically significant	xx (xx.x)	xx (xx.x)	xx (xx.x)
Cycle 2 Day 1	Clinically significant	xx (xx.x)	xx (xx.x)	xx (xx.x)
	Not clinically significant	xx (xx.x)	xx (xx.x)	xx (xx.x)
Cycle 2 Day 15	Clinically significant	xx (xx.x)	xx (xx.x)	xx (xx.x)
	Not clinically significant	xx (xx.x)	xx (xx.x)	xx (xx.x)
Cycle 3 Day 1	Clinically significant	xx (xx.x)	xx (xx.x)	xx (xx.x)
	Not clinically significant	xx (xx.x)	xx (xx.x)	xx (xx.x)
Cycle 3 Day 15	Clinically significant	xx (xx.x)	xx (xx.x)	xx (xx.x)
•	Not clinically significant	xx (xx.x)	xx (xx.x)	xx (xx.x)
Continue for all visit	ts			

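### The SAP gives no by-arm summary of TSH, T3 and T4, although the protocol has them monitored alongside liver enzymes on target-organ grounds

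*SAP*

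**What the plan says.** Protocol 3.4.5 states: "Monitoring of liver enzymes and levels of TSH, T3, and T4 in patients receiving tenalisib is recommended based on target organ toxicity". The tests sit in a panel defined in Table 5, footnote 9: "Chemistry Panel II includes total cholesterol, TG, LDL, HDL, T3, T4 and TSH". Table 5 marks that panel at screening, C1D1, C2D1, C3D1, the monthly visits from C4 and end of treatment. Footnote 19 adds: "All visits will be done monthly from Cycle 3 onwards for 24 months".

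SAP 8.8.3 plans descriptive statistics of absolute values and changes from baseline, by treatment group and overall, for "laboratory parameters(viz. Total bilirubin, Hemoglobin, Alkaline phosphatase, Platelet count, ALT, Total WBC, AST, Absolute neutrophil count, GGT, creatinine". The other laboratory data, including T3, T4, TSH, lipids, glucose and phosphorus, are to be listed. The section also says: "A separate listing of patients with abnormal laboratory test values will also be presented".

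Protocol 7.4.3 gives the route from a laboratory value to an adverse event: "Any grade 3 or 4 laboratory abnormalities and clinically significant grade 1 or 2 laboratory value(s) should be recorded as an AE". SAP 8.8.2 tabulates treatment-emergent adverse events by arm, term and maximum grade.

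**The concern.** Protocol 1.5.2 says the two arms exist to find which dose shows efficacy with acceptable safety. The safety analysis is descriptive, so the by-arm tables are the main evidence on that question. Of the two marker sets that 3.4.5 names on target-organ grounds, the liver tests get by-arm tables and the thyroid tests do not.

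At stake are shifts below the adverse event threshold: values that move out of range in several patients of one arm without any investigator calling them clinically significant. The trial is open label, so that call is made with the dose known. A reader of the study report would have to reconstruct the arm-level picture from listings.

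**Working it through.** The plan states no figure on this point, so the check is a count and a cross-reading.

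**1. Analytes collected** (Protocol Table 3, repeated in SAP 8.8.3). Hematology has 5, counting white cells with differential as one. Panel I has 16 and Panel II has 7 (total cholesterol, triglycerides, LDL, HDL, T3, T4, TSH). Total: 5 + 16 + 7 = 28.

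**2. Analytes summarised by arm** (SAP 8.8.3).

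| Set | Summarised | Collected |
|---|---|---|
| Hematology | 4 | 5 |
| Panel I | 6 | 16 |
| Panel II | 0 | 7 |
| All | 10 | 28 |

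Not summarised: 28 − 10 = 18. Bilirubin, ALP, ALT, AST and GGT are all in. Of the thyroid tests, 0 of 3 are.

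**3. Thyroid data available.** Sets up to Day 1 of cycle k = 1 (screening) + k. At C3D1 that is 1 + 3 = 4, and at C7D1 it is 1 + 7 = 8. Each is one fewer if the C1D1 draw is waived because screening fell within 72 hours. C7D1 is study day 1 + 6 × 28 = 169. The sample-size section assumes 20% without progression at 6 months, so about 0.20 × 20 = 4 patients per arm would supply data that late, if those without progression stay on treatment and the rest have stopped. Eight sets is therefore not typical, and late-cycle means would rest on very few patients.

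**4. Where a thyroid shift goes under the plan.**
- Grade 3/4, or Grade 1/2 judged clinically significant: recorded as an adverse event and counted by arm.
- Anything else: listed by patient, with treatment group, visit, result and the local lower and upper limits of normal (format of Listing 16.2.8.1.1, reused for biochemistry in Listing 16.2.8.2.1; I take Panel II to fall under biochemistry, since the index has no other place for it). No count, change or shift by arm is produced.

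**5. Could the table shell already cover it?** The shell for Table 14.3.2.1, reused for biochemistry in Table 14.3.2.2, says "Continue for all visits and parameters". SAP 7.1 also speaks generally of summarising continuous measures at each visit. Both are generic, whereas 8.8.3 names the analytes. The specific list is the natural instruction to follow, but the SAP should not leave the programmer to choose.

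**6. Metabolic analytes.** Protocol 1.4 reports hyperglycemia and hypertriglyceridemia at Grade 3 or higher in one patient each. It then says: "Hypophosphatemia and thrombocytopenia were reported in two patients", with no grade in that sentence. On the 169 exposed patients (the denominator for these counts is not stated, so this is an assumption), that is 1/169 = 0.6% and 2/169 = 1.2%. This is thin support.

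**The case against.** A reader might infer that thyroid and metabolic shifts never reach a comparison of the two doses. The documents do not support that. Severe or clinically significant values become adverse events and are tabulated by arm, and every value is listed with its treatment group. Only shifts not reported as adverse events lack a by-arm summary.

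A reader might also infer that the SAP breaks a protocol commitment to summarise these tests. It does not. Protocol 9.4.2 lets safety endpoints be listed, summarised or both, and 3.4.5 asks for monitoring, which Table 5 provides. Protocol 9.4.2 does plan a worst-grade tabulation for selected laboratory measurements, and the SAP output index has none. That is a separate gap, which a thyroid table would not by itself close.

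Three further objections have weight:
- The sentence after the thyroid recommendation in 3.4.5 names raised ALT/AST, rash and neutropenia as reported with tenalisib. The laboratory tests for these are all in the SAP list, and Protocol 1.4 names no thyroid event. But 1.4 gives only frequent related events and Grade 3 or higher findings, so it says little about low-grade thyroid change.
- A listing by patient and visit does show drift within a patient. It does not show how many patients per arm drift.
- Safety laboratories are local (Protocol 6.4), at about five centres, and T3/T4 units and assays are not specified. Pooled means may be hard to interpret. This stands, and it favours a shift table against local limits over means.

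**Conclusion.** The point holds in a limited form. TSH, T3 and T4 are named with liver enzymes on target-organ grounds and drawn every cycle, yet 0 of 3 enter a by-arm laboratory summary. What is lost is the arm-level view of shifts that are neither Grade 3/4 nor judged clinically significant. The same gap exists for glucose, triglycerides and phosphorus, with weaker grounds.

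This rests on reading the named list in SAP 8.8.3 as governing the generic table shell. It does not show that a thyroid effect exists or that the dose choice would change. No data are lost. It is an inexpensive improvement to the safety reporting.

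**What to change.** In SAP 8.8.3 and the output index, add TSH, T3 and T4 to the by-arm summaries, mainly as a shift table: baseline category (low, normal, high) against worst post-baseline category, using the local limits already carried in the listings. State how the worst value is chosen when a patient has both low and high results. Say in 8.8.3 whether the named list or the shell instruction decides the content of Table 14.3.2.2.

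As a lower priority, treat glucose, triglycerides and phosphorus the same way. Coverage would go from 10 to 10 + 3 = 13 of 28 analytes, then 13 + 3 = 16 of 28.

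The cost is one or two small tables from data already collected. The downside is small numbers, 20 per arm at most and fewer at later cycles. A worst-post-baseline shift limits this because it uses every patient with a baseline and at least one later value.

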9.4.2 Safety Analyses

The safety endpoints will include:

- Incidence of AEs and related AEs
- Incidence of grade 3 and grade 4 AEs
- Incidence of SAEs and death
- Laboratory values
- ECG/vital signs

The safety endpoints will be listed and/or summarized by dose cohort. No inferential statistical analyses will be performed. The analyses of safety will be based on the frequency of adverse events and their severity for patients in each portion who received at least one dose of study treatment. Worst toxicity grades per patient will be tabulated for select adverse events and laboratory measurements by using NCI CTCAE criteria v5.0.

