5.2 Changes from the Analyses Planned in the Protocol

There were no changes in the analysis planned in the protocol of the study at the time of preparing this statistical analysis plan.

BASELINE, EFFICACY and Safety EVALUATIONS 6.

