32	Table	Table 14.3.1.5	Treatment-Related Serious TEAEs by System Organ Class and Preferred Term - Safety Analysis Set
33	Table	Table 14.3.1.6	Treatment-Emergent Adverse Events by System Organ Class, Preferred Term and maximum CTCAE grade - Safety Analysis Set
34	Table	Table 14.3.1.7	Treatment-Related TEAEs by System Organ Class, Preferred Term and maximum CTCAE grade - Safety Analysis Set
35	Table	Table 14.3.1.8	Summary of Deaths by System Organ Class and Preferred Term - Safety Analysis Set
36	Table	Table 14.3.1.9	Treatment-Emergent Adverse Events leading to Dose Reduction or Interruptions by System Organ Class and Preferred Term – Safety Analysis Set
37	Table	Table 14.3.1.10	Treatment-Related TEAEs leading to Dose Reduction or Interruptions by System Organ Class and Preferred Term- Safety Analysis Set
38	Table	Table 14.3.1.11	Treatment-Emergent Adverse Events leading to Discontinuation of Study Drug by System Organ Class and Preferred Term- Safety Analysis Set
39	Table	Table 14.3.1.12	Treatment-Related TEAEs leading to Discontinuation of Study Drug by System Organ Class and Preferred Term- Safety Analysis Set
40	Table	Table 14.3.2.1	Descriptive Summary of Hematology parameters - Safety Analysis Set
41	Table	Table 14.3.2.2	Descriptive Summary of Biochemistry parameters - Safety Analysis Set
42	Table	Table 14.3.3.1	Descriptive Summary of Vital Signs - Safety Analysis Set
43	Table	Table 14.3.4.1	Descriptive Summary of ECG - Safety Analysis Set
44	Table	Table 14.3.4.2	Summary of Abnormal ECG results - Safety Analysis Set
45	Table	Table 14.3.5.1	Summary of ECOG Performance Status - Safety Analysis Set
46	Table	Table 14.3.6.1	Duration of Treatment Exposure and Compliance - Safety Analysis Set
47	Table	Table 14.3.6.2	Duration of treatment exposure by type of metastasis – Safety Analysis Set
48	Listing	Listing 16.2.1.1	Screened patients - All Patients
49	Listing	Listing 16.2.1.2	Randomization - All Enrolled Patients
50	Listing	Listing 16.2.1.3	Eligibility Review - All Patients

CONFIDENTIAL Page 24 of 106 ST-AD-032 version 01

51	Listing	Listing 16.2.1.4	Reasons for Withdrawal of Patient from the Study – Safety Analysis Set
52	Listing	Listing 16.2.1.5	Patient Visits - All Patients
53	Listing	Listing 16.2.2	Protocol Deviations during the Study - Safety Analysis Set
54	Listing	Listing 16.2.3	Analysis Populations - All Patients
55	Listing	Listing 16.2.4.1	Demography Data - Safety Analysis Set

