Table 14.3.1.11 Treatment-Emergent Adverse Events leading to Discontinuation of Study Drug by System Organ Class and Preferred Term Table 14.3.1.12 Treatment-Related TEAEs leading to Discontinuation of Study Drug by System Organ Class and Preferred Term

Protocol RP6530-1802

Table 14.3.1.6

Treatment-Emergent Adverse Events by System Organ Class, Preferred Term and maximum CTCAE grade Safety Analysis Set

System Organ Class	CTCAE	Tenalisib 800 mg BID	Tenalisib 1200 mg BID	Overall
Preferred Term	Grade	(N=xx)	(N=xx)	(N=xx)
		n (%), E	n (%), E	n (%), E
At least one TEAE	Total	x (xx.x), xx	x (xx.x), xx	x (xx.x), xx
	1	x (xx.x), xx	x (xx.x), xx	x(xx.x), xx
	2	x (xx.x), xx	x (xx.x), xx	x (xx.x), xx
	3	x (xx.x), xx	x (xx.x), xx	x (xx.x), xx
	4	x (xx.x), xx	x (xx.x), xx	x (xx.x), xx
	5	x (xx.x), xx	x (xx.x), xx	x (xx.x), xx
Blood and lymphatic system disorders	Total	x (xx.x), xx	x (xx.x), xx	x (xx.x), xx
	1	x (xx.x), xx	x (xx.x), xx	x (xx.x), xx
	2	x (xx.x), xx	x (xx.x), xx	x (xx.x), xx
	3	x (xx.x), xx	x (xx.x), xx	x (xx.x), xx
	4	x (xx.x), xx	x (xx.x), xx	x (xx.x), xx
	5	x (xx.x), xx	x (xx.x), xx	x(xx.x), xx
Etc				

Percentages are based on the total number of patients (N) in each treatment group.n: Number of patients with any event, E: Number of events, CTCAE: Common Terminology Criteria for Adverse Events, TEAE: Treatment-Emergent Adverse Event

If a patient has two or more adverse events in the same system organ class (or with the same preferred term) with different CTCAE grades, then the event with the highest grade is considered for that patient.

Treatment-Emergent Adverse Events are coded using MedDRA (version 24.0).

System organ classes are sorted in alphabetical order. Preferred terms are sorted within system organ class by descending order of frequency of overall preferred terms.

Treatment-Emergent Adverse Events are those that start on or after the date of first dose of study drug.

CTCAE Grade: 1=Mild, 2=Moderate, 3=Severe, 4=Life threatening, 5=Death

Reference Listing 16.2.7.1

Program: xx.sas Table Generation: ddmmmyyyy hh:mm:ss

Use same format for

CONFIDENTIAL

Page 53 of 106 ST-AD-032 version 01

Table 14.3.1.7 Treatment-Related TEAEs by System Organ Class, Preferred Term and maximum CTCAE grade - Safety Analysis Set

Protocol RP6530-2101

Table 14.3.2.1

Descriptive Summary of Hematology parameters

Safety Analysis Set

Parmeter (unit): xxxxxxx (xxx)

	Tenali	sib 800 mg BID	Tenal	lisib 1200 mg BID		Overall
		(N=xx)		(N=xx)		(N=xx)

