^{*:} Non-treatment-emergent adverse events

Use same format for

Document Date: 12MAY2023.

<Note to Programmer: Please add the footnote "Treatment-Emergent Adverse Events are those that start on or after the date of first dose of study drug.">

Listing 16.2.7.2 Treatment-Related TEAEs - Safety Analysis Set

Listing 16.2.7.3 Treatment-Emergent Grade 3, 4 and 5 Adverse Events - Safety Analysis Set

Listing 16.2.7.4 Treatment-Related Grade 3, 4 and 5 TEAEs - Safety Analysis Set

Listing 16.2.7.5 Treatment-Emergent Serious Adverse Events - Safety Analysis Set

Listing 16.2.7.6 Treatment-Related Serious TEAEs - Safety Analysis Set

Listing 16.2.7.7 Treatment-Emergent Adverse Events leading to Discontinuation of study drug - Safety Analysis Set

Listing 16.2.7.8 Treatment-Emergent Adverse Events leading to death - Safety Analysis Set

Page 86 of 106

ST-AD-032 version 01

Protocol RP6530-2101 Listing 16.2.8.1.1 Clinical Laboratory Evaluations – Hematology Safety Analysis Set Page xx of yy

Patient ID	Treatment Group	Visit	Date/Time of Collection	Test Name	Result	Unit	LLN	ULN	Normal/Abnormal	In case of CS, Specify AE No
Xxxx	Xxxxxx	Screening	DDMMMYYYY/ hh:mm	Xxxx	XX.X	XX	XX.X	XX.X	Normal	5
				Xxxx	xx.x	XX	XX	XX	Abnormal, NCS	

NCS: Not Clinically Significant; CS: Clinically Significant; EOT: End of Treatment; Clinical significance is applicable if results are out of reference range; LLN: Lower Limit of Normal; ULN: Upper Limit of Normal

Program: xx.sas Listing Generation: ddmmmyyyy hh:mm:ss

Use same format for

Document Date: 12MAY2023.

Listing 16.2.8.2.1 Clinical Laboratory Evaluations - Biochemistry - Safety Analysis Set

Page 87 of 106 ST-AD-032 version 01

Protocol RP6530-2101 Listing 16.2.8.1.2 Abnormal Laboratory Values – Hematology Safety Analysis Set Page xx of yy

Patient Treatment ID Group	Visit	Date/Time of Collection	Test Name	Result	Unit	LLN	ULN	Clinically Significant?	In case of CS, Specify AE No
Xxxx Xxxxx	Screening	DDMMMYYYY/hh:mm	Xxxx	XX.X	XX	XX.X	XX.X	No	_
			Xxxx	XX.X	XX	XX.X	XX.X	No	
			Xxxx	XX.X	XX	XX.X	XX.X	No	
			Xxxx	XX.X	XX	XX.X	XX.X	No	
	Cycle 1 Day	1 DDMMMYYYY/hh:mm	Xxxx	XX.X	XX	XX.X	XX.X	No	
			Xxxx	XX.X	XX	XX.X	XX.X	No	
			Xxxx	XX.X	XX	XX.X	XX.X	Yes	
			Xxxx	XX.X	XX	XX.X	XX.X	No	

CS: Clinically Significant; EOT: End of Treatment; Clinical significance is applicable if results are out of reference range; LLN: Lower Limit of Normal; ULN: Upper Limit of Normal; AE: Adverse Event.

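### The SAP omits the table of worst CTCAE grade per patient for laboratory measurements that protocol 9.4.2 promises, and SAP 5.2 declares no change

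*SAP*

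**What the plan says.** Protocol 9.4.2 lists laboratory values as a safety endpoint in their own right and states: "Worst toxicity grades per patient will be tabulated for select adverse events and laboratory measurements", graded by NCI CTCAE v5.0.

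SAP 8.8.3 names ten parameters, among them ALT, AST and absolute neutrophil count (ANC). It says their absolute and change-from-baseline values "will be presented using descriptive statistics (n, mean, median, standard deviation, minimum and maximum values) for each cycle", by treatment group and overall, with listings in addition. In the SAP section 12 output list the laboratory tables are 14.3.2.1 (haematology) and 14.3.2.2, the latter titled "Descriptive Summary of Biochemistry parameters - Safety Analysis Set". Their shared shell carries the footnote "Only scheduled visits are included in the table".

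The adverse-event half of the promise is kept. The shell for Table 14.3.1.6 says that when a patient has several events in the same class or term with different grades, "then the event with the highest grade is considered for that patient". Table 14.3.1.7 does the same for treatment-related events.

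SAP 5.2 states: "There were no changes in the analysis planned in the protocol of the study".

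**The concern.** The protocol names two things to be graded, and the SAP grades one of them without saying that the other has been dropped. A reader who relies on SAP 5.2 would expect a laboratory grade table in the study report and would not find it.

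The trial is meant to identify which of two doses has an acceptable safety profile (protocol 1.5.2), and protocol 3.4.5 singles out raised ALT/AST and neutropenia for monitoring. Means, standard deviations and extremes by cycle do not say how many patients on each dose reached each grade, and they do not follow a patient across cycles. The adverse event tables do count patients by grade, but in an open-label trial they depend on what the investigator judged reportable. The promised table would show the laboratory data independently of that judgement.

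**Working it through.** No figure in the plan needs to be reproduced. The check compares texts and counts outputs.

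**1. Count the outputs (SAP section 12).** Tables are items 1 to 47.
- Laboratory summary tables are items 40 and 41, so 2. Both are descriptive, with no grade in the shell.
- Tables by maximum CTCAE grade are items 33 and 34, so 2. Both are for adverse events.
- Tables that derive a grade from measured laboratory values: 0 of 47.
- Laboratory listings are items 78 to 83: 83 - 78 + 1 = 6 (pregnancy test not counted). Haematology and biochemistry shells show result, LLN, ULN and clinical significance, with the footnote "Clinical significance is applicable if results are out of reference range". Urinalysis shells show clinical significance only. Listings with a grade column: 0 of 6.

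**2. Trace what reaches the graded adverse event tables.** Protocol 7.4.3 says: "Any grade 3 or 4 laboratory abnormalities and clinically significant grade 1 or 2 laboratory value(s) should be recorded as an AE". It then keeps isolated abnormalities without clinical significance off the adverse event form if the investigator confirms this, and it lets a diagnosis stand in for the laboratory term.

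| Laboratory abnormality | In the graded AE tables? |
|---|---|
| Grade 3-4 | Yes, by 7.4.3 |
| Grade 1-2, clinically significant | Yes, by 7.4.3 |
| Grade 1-2, isolated, judged not significant | No |
| Part of a named diagnosis | The event appears, graded, under the diagnosis, but need not be counted under the laboratory parameter |

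The last two rows are the loss, together with the absence of any count that does not pass through investigator reporting.

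**3. Size of the loss.** The documents do not give it. As an assumption only: suppose 4 of 20 patients on a dose have a worst grade of 1-2 for some parameter, and a share *s* of them is judged not significant. Patients absent from the AE tables = 4 x *s*:
- *s* = 0: 0
- *s* = 0.25: 1
- *s* = 0.50: 2
- *s* = 0.75: 3

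If every abnormality is recorded, nothing is missed.

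**4. Scheduled visits.** Schedule footnotes 8 to 10 (protocol Table 5, repeated in SAP 6.1) foresee tests at supplementary visits, and protocol Table 7 asks for ALT/AST weekly or twice weekly during transaminitis. The laboratory summary tables leave such results out. The listing shells carry no such limit, and SAP 8.8.3 lists what is captured in the database. Whether unscheduled results were captured is not shown.

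**5. Which grading rule to use.** Protocol Table 7 cannot serve alone. For ALT/AST with a normal baseline it sets Grade 1-2 at >1-3 x ULN and Grade 3 at >5-20 x ULN, so values from 3 to 5 x ULN have no grade. It also switches to multiples of baseline when baseline is abnormal, and inclusion criterion 7e admits ALT/AST up to 5 x ULN with liver involvement. Take a patient at 4 x ULN at baseline and 6 x ULN at peak. Against ULN, 6 > 5, which is Grade 3. Against baseline, 6/4 = 1.5, which is the bottom of Table 7's Grade 1-2 band. The table therefore needs a stated baseline rule.

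**The case against.** The strongest reply is that the adverse event tables already do most of the work. Grade 3-4 and clinically significant lower-grade values go to the AE form, and SAP 8.8.2 counts each patient once per preferred term at maximum grade, by dose. Protocol 1.4 reports earlier tenalisib laboratory toxicity in this way, with ALT and AST increases given as adverse events. This stands for severe values, and it is why the point is limited.

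Two stronger readings are tempting, and the documents support neither.
- A reader might infer that severe liver toxicity could go uncounted, either because per-cycle summaries can look alike in two arms with different numbers above 5 x ULN, or because the exception in 7.4.3 for isolated abnormalities carries no grade limit of its own. But the preceding sentence in 7.4.3 requires any Grade 3 or 4 value to be recorded, so the natural reading confines the exception to low grades, and the AE tables would separate such arms.
- A reader might take the earlier related-event rates in protocol 1.4 as the size of the gap. Those are adverse event rates. They indicate what the AE tables capture, not what they miss.

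Other replies stand in part. The protocol says only select measurements, and protocol 9.1 allows methods to be revised in the SAP. That gives freedom over which parameters and methods to use, but it does not cover dropping the whole laboratory half while SAP 5.2 declares no change. With 40 patients, grades could be worked out by hand from the haematology and biochemistry listings, since baseline and later values are both shown. That is possible, but it is not the tabulation promised, and the SAP gives no rule for doing it.

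**Conclusion.** The point holds as an undeclared omission. The protocol promises a per-patient worst-grade tabulation for selected laboratory measurements, the SAP plans none, and SAP 5.2 says nothing has changed. The counts of 0 of 47 tables and 0 of 6 listings refer to grades derived from measured values. They do not mean that graded laboratory toxicity is absent from the report.

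The loss is mainly Grade 1-2 abnormalities judged not clinically significant, counts by laboratory parameter where a diagnosis was recorded instead, and a view of the data independent of investigator reporting. Its size is unknown and may be zero. This rests on sites following protocol 7.4.3 and on the SAP output list being complete. Safety is a secondary, descriptive objective, so no formal test or confidence interval is affected. The omission should be corrected because the protocol commits to the table and it is cheap to produce, but it does not threaten the trial's main conclusion.

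**What to change.** In SAP 8.8.3 add one table, by dose and overall, of worst post-baseline CTCAE v5.0 grade per patient for selected parameters, at least ALT, AST and ANC. Use all post-baseline results in the database, scheduled or not. Take the grade cut-offs and the baseline rule from CTCAE v5.0 rather than from protocol Table 7, and state them in the SAP. Keep Tables 14.3.2.1 and 14.3.2.2 and all adverse event tables as they are.

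If the table is not added, declare the omission in SAP 5.2 with a reason.

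Two extras go beyond what the protocol promises and are optional: setting the worst grade against baseline grade, and a row counting each patient once for any hepatic-enzyme adverse event term.

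The cost is one paragraph and one programmed table. Result, LLN and ULN are already in the haematology and biochemistry listing shells, and no new assessment is needed. The downside is one extra output.
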